#### Figure 1: Schematic Study Overview

D=Day, EoST/EoSA=end of study treatment/end of study assessments, FU=follow-up, V=Visit, W=Week.

Enrolled subjects will come to the clinical study center at screening (two visits from Day -28 to Day -1). Visit 2 of screening can only take place after confirmed IPF diagnosis on HRCT and LB (if applicable).

At Visit 3, eligible subjects will be randomized in a 1:1:1 ratio to receive GLPG1690 600 mg q.d., GLPG1690 200 mg q.d., or matching placebo for at least 52 weeks. Randomization will be stratified for background local standard of care for treatment of IPF.

Subjects will come to the clinical study center on Day 1 (baseline), Weeks 2, 4, 8, 12, 18, 26, 34, 42, 52, and every 12 weeks thereafter. Additional unscheduled visits are allowed if, in the investigator's opinion, further evaluation (clinical, laboratory, or other) is needed.

When the last subject reaches 52 weeks (Visit 12), subjects still taking IP and who had a scheduled visit at the clinical study center within 6 weeks before this date will be contacted by their investigator (phone call) to discontinue IP within 7 days after this date. Then the last scheduled visit will be documented as the end of study treatment (EoST) visit. These subjects will be invited to their follow-up visit scheduled at the clinical study center 4 weeks after their last dose of IP ( $\pm$ 7 days). For subjects still taking IP and who had their last scheduled visit more than 6 weeks before the date that the last subject reaches 52 weeks into the study (Visit 12), a scheduled visit will be planned within 2 weeks of this date for an EoST visit, followed by a follow-up visit 4 weeks later (visit at clinical center or phone call). Note that these subjects will continue IP intake until their EoST visit.

For subjects who, for any Coronavirus disease (COVID-19)-related reason, cannot perform study procedures, extended visit windows, the possibility to conduct phone/televisits and home (or other remote location) visits, and alternative assessment procedures are detailed in Section 6.1.1 of the CSP.

Subjects who discontinue IP early (early treatment discontinuation [ETD]), with the exception of patients lost to follow-up and patients who withdraw consent, will be encouraged to complete all following visits and evaluations as originally planned per protocol.

In particular, the subject will be requested if at all possible to attend:

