#### For endpoints not including vital status:

The last contact, not including mortality information is defined as the latest date collected in the eCRF from the date of death, visit dates, AE dates, concomitant treatment dates, drug intake dates or laboratory test dates, study completion date. Information from the vital status form is not to be taken into account for this calculation.

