# Censoring

Time to event endpoints are defined from the date of first dose of IP.

If the subject did not have an event, the time to event will be censored at the last contact date, as defined in Section 6.4.

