# 9.4.1.1. Treatment-Emergent Principle.

All adverse events starting on or after the first dose of IP and up to the last dose plus 30 days, are considered treatment-emergent adverse events (TEAE).

All AEs and changes in attributes (worsening and improvement) of AEs are reported in the database. Only worsenings of a pre-existing adverse event, after first dose of IP up to the last dose plus 30 days are to be considered as a TEAE, improvements after first dose of IP are not. A worsening is defined if at least one of the attributes of the events worsens (severity, seriousness, relationship or action taken).

Selected tables will also be created for all AEs (or worsenings) which started after the first dose of IP (till the end of the study). Adverse events starting before the first dose of IP and improvements will be excluded, but will be in the listings.

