# 9.4.1.6. Analyses

### 9.4.1.6.1. Treatment-emergent AEs during the treatment period

A summary table of the number of subjects with at least one TEAE, at least one IP/SOC related TEAE, one serious TEAE, a TEAE leading to death, TEAEs by worst severity, and TEAE leading to IP/ SOC discontinuation, down-titration and interruption per treatment group will be provided. The table will also include the difference in percentage of subjects with an TEAE from placebo for each of the two dose groups, together with the 95% CI using the method of Miettinen and Nurminen (Miettinen & Nurminen, 1985).

The number (percent) of subjects with a TEAE by system organ class and preferred term will be presented. Similar tables will be provided by worst severity, by IP/SOC relationship and, by worst severity and relationship. Furthermore serious TEAEs, deaths, TEAEs leading to IP/SOC down-titration, TEAEs leading to IP/SOC interruption and TEAEs leading to IP/SOC discontinuation will be tabulated by system organ class and preferred term.

A table will also be presented, with the difference from placebo and 95% CI based on the method of Miettinen and Nurminen for the number (percent) of subjects with a TEAE by system organ class and preferred term, for events with an incidence of at least 5% in at least one of the treatment groups (600, 200 mg or placebo).

Kaplan-Meier estimates will be presented graphically and in tabular format for the following time to first event endpoints, by treatment, as well as by treatment and stratum:

- first TEAE
- first serious TEAE
- first TEAE leading to early IP discontinuation

Treatment-emergent COVID-19 infections and suspected infections will be tabulated and listed.

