# 9.4.2.8. Analyses

No formal inferential statistics (p-values) will be derived.

For each laboratory test, descriptive statistics and graphical presentation (line plot of the mean and SE) will be provided for the actual laboratory values and change from baseline over time-by-treatment group.

A summary table per laboratory test category (hematology, biochemistry, urinalysis and coagulation), laboratory test and unit, treatment group and time point, showing only the mean value of actual values and changes from baseline will also be provided.

All laboratory abnormalities after the first dose of IP up to 30 days after the last dose will be included, consistently with AE reporting.

A shift table per laboratory test category (hematology, biochemistry, urinalysis and coagulation), laboratory test and treatment group will be provided for laboratory tests with normal ranges, for which CTCAE grades are not available. The table will present the worst shift in abnormality (L/N/...) during the treatment period versus the baseline abnormality (L/N/H).

Frequency table will be provided of the worst treatment-emergent laboratory abnormalities per laboratory test category (hematology, biochemistry, urinalysis and coagulation), laboratory test, and treatment group. This table will be created for those laboratory tests for which CTCAE grades are not available.

A shift table per laboratory test category (hematology, biochemistry and coagulation), laboratory test and treatment group for CTCAE grades will also be provided for selected tests only. The table will present the worst shift in CTCAE toxicity grade during the treatment period versus the baseline value.

A frequency table of the worst treatment-emergent laboratory CTCAE toxicity grades per laboratory test category (hematology, biochemistry and coagulation), laboratory test, and treatment group will be provided for selected tests only.

Shift table per laboratory test category (hematology, biochemistry, and urinalysis), laboratory test, and treatment group for laboratory tests with categorical data. The table will present the worst shift in value during the treatment period versus the baseline value.

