#### 9.4.2.9. Elevated Liver Function Test

Time to first liver enzyme elevation in conjunction with bilirubin elevation (alanine aminotransferase (ALT) and/or aspartate aminotransferase (AST)  $\geq$ 3x upper limit of normal (ULN) and bilirubin  $\geq$  1.5xULN) will be presented by a graph and table.

A graphical and tabular presentation (Kaplan-Meier) of the time to first liver enzyme elevations (per level) as defined in the protocol, ALT and/or AST

- $\geq 1.5 \text{xULN}$
- $\geq$  3xULN
- $\geq$  5xULN
- $\geq 8 \text{xULN}$

In addition a similar shift table and frequency table as for the CTCAE grades defined in Section 9.4.2.8 will be provided using the grades shown below:

Tests	Thresholds
AST/ALT combination	AST 1.5 - <3 x ULN AST >= 3 - <5 x ULN AST >= 5 - <8 x ULN AST >= 8 x ULN
	ALT 1.5 - <3x ULN ALT >= 3 - <5 x ULN ALT >= 5 - <8 x ULN ALT >= 8 x ULN
	AST and/or ALT 1.5 - <3 x ULN AST and/or ALT >= 3 - <5 x ULN AST and/or ALT >= 5 - <8 x ULN AST and/or ALT >= 8 x ULN

Tests	Thresholds	
AST/ ALT / bilirubin combination	Bilirubin >= 1.5 x ULN and AST or ALT >= 3 x ULN	
	Bilirubin $\geq 2 \ge 0$ ULN and AST or ALT $\geq 3 \ge 0$	

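### The Kaplan-Meier curves for treatment-emergent adverse events have no stated censoring rule, and the only one the SAP defines, last contact, would understate on-treatment risk

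*SAP*

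**What the plan says.** SAP 9.4.1.1 defines TEAEs as "All adverse events starting on or after the first dose of IP and up to the last dose plus 30 days". Table 1 in SAP 6.2 closes the treatment period at the same point and puts later events in follow-up. SAP 9.4.1.6.1 then plans the curves: "Kaplan-Meier estimates will be presented graphically and in tabular format for the following time to first event endpoints, by treatment", for first TEAE, first serious TEAE and first TEAE that leads to stopping IP. It does not say when an event-free subject is censored.

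The SAP has one censoring date. Section 6.5, whose title refers to censoring rules, states for endpoints without vital status: "The last contact, not including mortality information is defined as the latest date collected in the eCRF". The dates that feed it include visits, AEs, concomitant treatments and laboratory tests, so it is not tied to last dose. Sections 9.3.3 and 9.3.4 apply it: "If the subject did not have an event, the time to event will be censored at the last contact date". Section 9.3.4 cites Section 6.4 for the definition, but 6.4 defines baseline.

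SAP 2.3 (like protocol 4.1 and 4.5.4) says that subjects who stop IP early, unless lost to follow-up or withdrawing consent, "will be encouraged to complete all following visits and evaluations as originally planned per protocol".

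For liver enzymes, SAP 9.4.2.9 plans "A graphical and tabular presentation (Kaplan-Meier) of the time to first liver enzyme elevations (per level) as defined in the protocol", also without a censoring rule. The 30-day limit appears one section earlier, in 9.4.2.8: "All laboratory abnormalities after the first dose of IP up to 30 days after the last dose will be included, consistently with AE reporting".

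**The concern.** A Kaplan-Meier risk set should contain only subjects in whom the event could still be counted. Once a subject is more than 30 days past the last dose, no TEAE can count. If that subject is carried to last contact, time without possible events goes into the denominator and the estimated risk falls.

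The effect grows with the share of subjects who stop IP and stay in the study. If one arm has more early discontinuation, its curve is lowered more, and a dose that more subjects stop can look safer than it is. The point matters because safety is among the analyses kept after the studies were halted on benefit-risk (SAP 1 and 9.1), and the omission list in 9.1 does not remove these curves. The AE tables in 9.4.1.6.1 and 9.4.1.6.2 are crude percentages, so within the AE section the curves carry the adjustment for time.

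**Working it through.** The documents give no figure for these curves, so there is nothing to reproduce.

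**Inputs from the documents.** Counting window: first dose to last dose + 30 days (SAP 9.4.1.1). Available censoring date: last contact (SAP 6.5). Planned treatment: 52 to about 132 weeks (SAP 2.3). Arm size: 250.

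**Inputs assumed, because the documents do not give them.** Event hazard, rate of stopping IP, and share of stoppers who stay in the study.

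**Step 1: direction.** The estimate is 1 − ∏(1 − d/n) over event times. Both censoring rules count the same events d. Last contact can only make the numbers at risk n larger. Each factor is therefore at least as large, and the estimated risk cannot be higher than with window censoring. It is lower whenever an event follows the closing of some retained subject's window.

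**Step 2: size by formula.** Let λ be the event hazard, μ the hazard of stopping IP (independent of the event), w = 30/365.25 = 0.0821 years, and let all stoppers stay.

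- Censored at window end, the estimate targets 1 − e^(−λt).
- Censored at last contact, it targets [1 − e^(−λw)] + λ/(λ+μ) × e^(μw) × [e^(−(λ+μ)w) − e^(−(λ+μ)t)].

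With λ = 0.20 and μ = 0.50 per year:

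- One year: 0.0163 + 0.2857 × 1.0419 × (0.9441 − 0.4966) = 0.0163 + 0.1332 = 15.0%, against 1 − e^(−0.2) = 18.1%.
- Two years: 0.0163 + 0.2857 × 1.0419 × (0.9441 − 0.2466) = 0.0163 + 0.2076 = 22.4%, against 1 − e^(−0.4) = 33.0%.

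A simulation of 400,000 subjects, with study end uniform over 52–132 weeks, gave 15.0% and 22.5% for last contact, and 18.2% and 33.1% for window censoring.

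**Step 3: a less extreme setting.** Simulated with λ = 0.3 per year, 80% of stoppers staying, and 25% stopping IP by Week 52:

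| | Window end | Last contact | Shortfall (points) |
|---|---|---|---|
| Week 52 | 25.9% | 23.6% | 2.3 |
| Week 104 | 45.0% | 37.4% | 7.6 |

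Over hazards of 0.2–0.4 and discontinuation of 15–35%, the shortfall is about 1 to 4 points at Week 52 and 3 to 13 at Week 104. The early halt does not remove it: with follow-up assumed uniform over 10–110 weeks, the 25% case gives 25.9% against 23.7%, and 45.3% against 37.7%.

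**Step 4: unequal discontinuation.** With equal true hazards (0.3), but 15% stopping on placebo and 35% on active, last contact shows 24.5% against 22.5% at Week 52 and 40.4% against 34.0% at Week 104. These are false advantages of 2.0 and 6.4 points for active. Ignoring censoring, the standard error of the Week 52 difference at 250 per arm is √(0.245×0.755/250 + 0.225×0.775/250) = 3.8 points, so 2.0 points is about 0.5 SE. At Week 104 it is √(0.404×0.596/250 + 0.340×0.660/250) = 4.3 points, so 6.4 points is at most 1.5 SE; censoring makes the SE larger.

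**Step 5: discontinuation caused by the event.** Steps 2–4 treat stopping as independent of the event. A subject who stops because of the event has already left the risk set and adds no bias. If half of Week 52 discontinuation is of that kind (assumed), the shortfall in the 25% case drops to about 1.0 point at Week 52 and 3.8 at Week 104. The contrasts in Step 4 drop to about 1.0 and 3.2 points.

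**The case against.** The strongest reply is that the SAP does not say these curves are censored at last contact. The instruction appears only in 9.3.3 and 9.3.4, both under efficacy. Where Section 6.5 is wanted elsewhere, as for time in study in 9.2.2, it is cited; 9.4.1.6.1 and 9.4.2.9 do not cite it. The heading of 9.4.1.6.1 refers to the treatment period, which Table 1 ends at last dose plus 30 days, and SAP 1 leaves technical derivations to a separate document. This stands: a reader might infer that the SAP prescribes a wrong risk set, and the text does not go that far. It leaves the rule open and offers only one date to fill the gap.

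A reader might also take these curves as the only time-adjusted view of harm. They are not: 9.3.3.1 plans Kaplan-Meier and Cox analyses of mortality, all-cause hospitalization and acute exacerbation. The safety curves are descriptive, since 9.4 excludes formal testing.

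Nor is window censoring neutral. It treats stopping IP as uninformative, although protocol 4.5.4 ends treatment for several safety findings. Last-contact censoring comes close to a cumulative incidence with IP discontinuation as a competing event. That is a legitimate target if declared, but the SAP does not declare it. The objection is strongest for the first TEAE that leads to stopping IP, where stopping for another reason is a true competing event.

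Finally, the extension to liver enzymes and to 9.4.1.6.4 is less secure. Section 9.4.2.9 does not repeat the 30-day limit stated in 9.4.2.8, and 9.4.1.6.4 does not call its events treatment-emergent. If no window applies there, last contact is the right date.

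**Conclusion.** The point holds as a gap with a predictable consequence. The TEAE curves lack a censoring rule, and applying the only one in the SAP would understate on-treatment risk, more so in the arm with more early discontinuation. The direction needs no assumption about rates. The size does: the ranges in Step 3 rest on constant hazards, 80% retention off drug and discontinuation independent of the event, and they shrink as in Step 5 when the event itself prompts stopping. The effect is small for first TEAE if most first events come early, and negligible for subjects on IP to study end, whose follow-up visit is 4 weeks after treatment ends.

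A reader might go further and conclude that the reported comparison favours an active dose. The documents give no discontinuation rates by arm, so this cannot be said; Step 4 shows only what unequal rates would do.

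**What to change.** Add to SAP 6.5 and 9.4.1.6.1: in time-to-event analyses of TEAEs, event-free subjects are censored at the earlier of last dose of IP plus 30 days and last contact.

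- For 9.4.1.6.4 and 9.4.2.9, first state whether events are limited to that window (9.4.2.8 suggests so for laboratory abnormalities). Apply the same rule only if they are, and keep last contact where events count to the end of the study.
- For the first TEAE that leads to stopping IP, label the curve as on-treatment risk, or use cumulative incidence with other reasons for stopping as the competing event.
- Correct the cross-reference in 9.3.4 from Section 6.4 to Section 6.5.

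The cost is a few sentences and one changed censoring variable. The downside is that numbers at risk fall faster, so late estimates are less precise.

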#### 9.4.1.6.2. AEs from First Dose of IP up to the End of the Study

A summary table of the number of subjects with at least one AE, at least one IP/SOC related AE, one serious AE, an AE leading to death, AEs by worst severity, and AE leading to IP/SOC discontinuation, down-titration and interruption per treatment group will be provided for all AEs starting after the first dose of IP (up to the end of the study). The table will also include the difference in percentage of subjects with an AE from placebo for each of the 2 dose groups, together with the 95% CI using the method of Miettinen and Nurminen.

The number (percent) of subjects with an AE by system organ class and preferred term will also be presented, for AEs, deaths, SAEs, AEs leading to IP/SOC discontinuation down-titration and interruption.

A table will also be presented, with the difference from placebo and 95% CI based on the method of Miettinen and Nurminen for the number (percent) of subjects with an AE by system organ

class and preferred term, for events with an incidence of at least 5% in at least one of the treatment groups (600, 200 mg or placebo).

COVID-19 infections and suspected infections will also be tabulated and listed.

Listings will be provided for the serious adverse experiences (including AEs leading to hospitalization), deaths, AEs leading to death and AEs leading to down-titration, interruption and early treatment discontinuation of IP, Pirfenidine and Nintedanib.

#### 9.4.1.6.3. EudraCT Adverse Events Reporting

For the purpose of EudraCT reporting, the following frequency tabulations will be added:

Frequency tabulations, by system organ class and preferred term, of the number (percent) of subjects with serious TEAE and the number of serious TEAEs will be presented. A similar table will be provided for the all non-serious TEAEs and for non-serious TEAEs reported in at least 5% of the subjects in any treatment group.

#### 9.4.1.6.4. Adverse Events Related to Nintedanib or Pirfenidone

To investigate the events expected to be associated with pirfenidone and nintedanib, Kaplan-Meier curve and table, as well as a counts table by system organ class and preferred term, by treatment, as well as by stratum and treatment will be provided for the preferred terms of events of specific interest to nintedanib (e.g. diarrhea, nausea, vomiting, dehydration, weight decrease and decreased appetite adverse events) and pirfenidone (e.g. photosensitivity reactions, nausea, diarrhea, dyspepsia, vomiting, gastro-esophageal reflux disease, and abdominal pain). The full list of preferred terms to be investigated will be detailed before unblinding for the CSR.

#### 9.4.1.7. Subgroup Analyses

For each subgroup, a summary table of the number of subjects with at least one TEAE, at least one related TEAE, a serious TEAE, leading to death, TEAEs by worst severity, and TEAE leading to down-titration, interruption and discontinuation of IP/SOC per treatment group will be provided. The number (percent) of subjects with a TEAE by system organ class and preferred term will also be presented per subgroup.

The following subgroups will be investigated:

- Age (<65 and  $\geq$ 65 years),
- Race,
- Sex,
- Stratum,
- Geographic region (NA, EMEA, Latin-America, Asia-Pacific)

Since the two studies are identically designed, more subgroups may be investigated in the pooled safety analysis in the ISS/SCS to increase the size of small subgroups.

# 9.4.2. Laboratory Safety

Since all scheduled clinical laboratory evaluations will be performed by the central laboratory, only data from the central laboratory will be included, information from local labs will not be used. Lab tests that are not part of the planned test panels according to the protocol will only be listed.

